4. PARTICIPANT ELIGIBILITY

4.1 Description of sites enrolling participants: Caregivers of infants ages 1-12 months old will be recruited from one of the five the Children's Health Centers (CHCs) at Children's National Health System. These health centers together treat ~30% of all children ages 0-18 years old in DC with Medicaid insurance. The population is predominantly minority (African American (85%), Hispanic (8%)) and publically insured (83%).

4.2 Inclusion criteria: Caregivers will be eligible if they can read English at the 8th grade level, and have reliable access to the internet and email for 7 weeks. English proficiency and internet access will be verified by parental completion of the first online survey within 24 hours of the request. Caregivers must also be a custodial guardian of an infant between the ages of 1-12 months old who lives with them, currently wears diapers, and has had \geq 1 diaper rash in the 2 months preceding recruitment.

4.3 Exclusion criteria: Caregivers will be excluded if their infant is immunocompromised, has a congenital disorder, or, on the day of recruitment, has a diaper rash, has a moderate to severe illness requiring hospitalization or transfer to the emergency room, or was circumcised <10 days prior. Participants who do not complete the first online survey or ≥2 post-intervention online surveys will be excluded from participating in the remainder of the study. They will also be excluded if they do not have a stable address at which they can receive a package of Theraworx at week 4 and/or are unable to pick it up at Children's National.

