5.3.2 Weekly, online surveys: Starting on the first Monday morning that falls at least 8 days from completion of the baseline, in-person survey and repeating each of the following Monday mornings for a total of 7 occurrences, a unique online survey link will be emailed to each participant. Each Sunday beforehand, participants will be texted and emailed a reminder to check their emails the next day and to complete the survey within 24 hours of receiving the emailed link. Each Monday morning, participants will receive a second text message reminder. By each Tuesday at noon, a list will be generated of survey non-respondents who will be contacted by phone twice that day by study staff to complete that week's survey on the phone. Each Wednesday morning, ClinCards will be charged with incentive awards for participants who complete the entire online survey. Participants who do not complete at least the first online survey will not be eligible to complete any further surveys and will be dropped from the study. This will help limit participation to those who can demonstrate capacity and willingness to complete the online survey with the intent of minimizing loss-to-follow up over the 7-week period of individual enrollment.

Weekly online surveys will assess whether the infant had any diaper dermatitis over the past 7 days, and if so, the total number of days with rash, and severity of rash on its worst day (using a modified Diaper Dermatitis Scale score (0-8)). It will also assess for any: use of other products and adjuvant therapies in the diaper area, diarrheal illnesses, new foods initiated, and changes to their contact information. The surveys during the run-in period (weeks 1-3) will confirm whether the participant prefers to pick up the Theraworx or have it sent to their home (Appendix F). During the trial period (weeks 4-6), the weekly survey will also assess how frequently Theraworx was used, and whether it was applied as a foam and/or spray (Appendix G). The final survey at the end of week 7 will be slightly longer since it will also assess satisfaction with Theraworx (in terms of its smell, feel, appearance, ease of use, whether they would recommend it to a friend, and how it compares to other diaper creams they have used) (Appendix F).

5.4 Participant reimbursement: To promote completion of online surveys and reduce risk of participant loss-to-follow up, an escalating incentive scale will be used. Completion of the baseline, in-person survey and the

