7.2 Stopping Criteria

7.2.1 Individual Stopping Criteria

- All protocol interventions are complete
- Failure to complete the first online survey or ≥2 post-intervention online surveys
- Death
- Lost to follow-up
- Study withdrawal
- Serious Adverse Event
- Discretion of the Study PI, such as the PI decides that continuing in the study would be harmful or no longer in the participant's best interest

7.2.2 Study stopping criteria:

- The data show a significantly increased risk of serious adverse effects during the experimental phase of the study.
- It becomes clear that successful completion of the study is not feasible (e.g. there is an excess of patient dropout, missing data, lack of recruitment, etc).

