9.3 Statistical Considerations

Hypothesis 1a: Parents will report fewer total days of diaper dermatitis in their infants when the infants are using Theraworx than when they are not. To evaluate Hypothesis 1a, total reported dermatitis days over the 4 week pre- and post-intervention time-points will be separately summed. For the primary analysis, only participants who completed all 8 weekly surveys will be included. Secondary analyses may consider all participants with at least two reports in each of the study periods, with missing values assumed to be the mean number of dermatitis days reported by the participant by study period. Number of dermatitis days during usual care (pre-intervention) will be compared to number of dermatitis days following use of the Theraworx Spray Foam (post-intervention) using either paired t-test or Wilcoxon signed rank test, as appropriate.

Hypothesis 1b: Parents will be less likely to report any diaper dermatitis in their infants when the infants are using Theraworx than when they are not. Occurrence of any dermatitis during the two study periods will be coded as "yes" (at least one dermatitis day) or "no" (zero dermatitis days) based on parent report of number of dermatitis days. Differences in occurrence pre- and post-intervention will be explored using McNemar's test. If numbers permit, conditional logistic regression will be considered to evaluate odds of dermatitis when using Theraworx Spray Foam compared to usual care.

Hypothesis 2a: Parents will report less use of adjuvant topical treatments (antifungals, antibacterials, steroids) for their infant's diaper dermatitis when they are using Theraworx than when they are not. Use of adjuvant topical treatments during each of the study periods will be considered as both a binary variable (any or none) as well as frequency of use, defined as number of weeks in which use was reported. Any use pre- vs. post-intervention will be evaluated using McNermar's test or conditional logistic regression. Number of uses will be compared using Wilcoxon signed rank test. Depending on numbers, marginal homogeneity tests may also be considered, treating the number of weeks as categorical variables. As use during unreported weeks will be unknown and difficult to quantify, primary analyses will consider only participants who completed all surveys.

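### The primary analysis of Hypothesis 1a discards families that stay in the study after missing one survey, and the analyses that would use their data are only optional

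*Combined protocol and SAP*

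**What the plan says.** - **Analysis set.** Section 9.3, Hypothesis 1a: "For the primary analysis, only participants who completed all 8 weekly surveys will be included". The outcome is a sum per period: "total reported dermatitis days over the 4 week pre- and post-intervention time-points will be separately summed". Hypothesis 2b repeats the completer rule. Hypothesis 2a applies it too and is the only place that gives a reason: "As use during unreported weeks will be unknown and difficult to quantify, primary analyses will consider only participants who completed all surveys". Hypothesis 1b states no such limit.
- **Who stays in.** Section 4.3: "Participants who do not complete the first online survey or ≥2 post-intervention online surveys will be excluded from participating". Section 7.2.1 lists the same condition as an individual stopping criterion: "Failure to complete the first online survey or ≥2 post-intervention online surveys". Section 5.3.2 repeats the part about the first survey: "Participants who do not complete at least the first online survey will not be eligible to complete any further surveys".
- **What could use incomplete reporters.** Hypothesis 1a: "Secondary analyses may consider all participants with at least two reports in each of the study periods", with missing weeks set to the participant's own mean for that period. The end of section 9.3 adds that GEE models on weekly outcomes may be considered. Neither is a commitment.
- **Sample size.** Section 9.2 needs 65 participants measured at both time-points, for a 2-day difference with SD up to 5 days and moderate correlation, at 80% power and two-sided 0.05. It recruits 100 to allow for 35% loss to follow-up, and would consider 150 if loss exceeds that at the interim.

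**The concern.** The rule for staying in the study and the rule for entering the primary analysis do not match. A family that misses one later survey is kept, surveyed and paid, then left out of the comparison the trial was built for.

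Two things are at stake. The first is precision: reports already collected do not contribute, so the confidence interval for the 1a difference is wider than it needs to be. The second is selection: four of the eight required reports fall after the product starts, so membership of the primary set depends partly on behaviour on treatment. In an open-label, parent-reported, before-and-after study, missing a survey could be related to rash or to perceived benefit.

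Because the alternatives are optional, whether to run and report them could also be decided after the primary result is known.

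**Working it through.** **1. The plan's own numbers reproduce.** For a paired t-test, SD of the difference = SD × √(2(1 − ρ)). Section 9.2 gives no value for ρ. With SD 5, a 2-day difference and a noncentral t calculation, ρ = 0.35 needs 66 and ρ = 0.40 needs 61. The usual Wilcoxon inflation takes the latter to 61 × π/3 ≈ 64. So 65 fits ρ of about 0.35 to 0.40. Recruitment: 65 / (1 − 0.35) = 100. I use ρ = 0.4 below, where the SD of the difference is 5 × √1.2 = 5.48 and 65 pairs give 82.6% power by the t-test.

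**2. Who is retained.** I read the eight surveys as baseline plus seven online, giving four reports per period (the baseline survey in 5.3.1 asks for rash days over the last 7 days). The post-intervention condition can mean missing two or more, or completing fewer than two. A family that misses one survey after the first online survey stays in on either reading, with 3 of 4 reports in one period and 4 of 4 in the other.

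**3. How many are dropped.** The documents give no response rate, so p, the chance of completing each online survey, is an assumption. With independent misses, no other dropout, and stopping at the second missed post-intervention survey:

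- Completers = p^7
- Never stopped = p × [p^4 + 4(1 − p)p^3]
- Retained non-completers = the difference

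At p = 0.90: 0.90^7 = 0.478; 0.90 × (0.6561 + 0.2916) = 0.853; difference 0.375.

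Per 100 enrolled (differences taken before rounding):

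| Response per survey | Completers | Never stopped | Retained but dropped | At least two reports per period |
|---|---|---|---|---|
| 98% | 86.8 | 97.8 | 11.0 | 97.9 |
| 95% | 69.8 | 93.7 | 23.8 | 94.3 |
| 90% | 47.8 | 85.3 | 37.5 | 87.5 |
| 90%, ICC 0.3 | 68.6 | 84.1 | 15.5 | 86.1 |

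If the rule means completing fewer than two, the 90% figure rises from 37.5 to 41.8. If baseline is not counted as a report, the two-report set is 97.8, 94.1 and 86.6 at 98%, 95% and 90%.

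**4. Precision.** The SE ratio is (SD of the difference, two-report set ÷ completers) × √(completers ÷ two-report set). At 90% response, simulation with week-to-week correlation of 0.2 to 0.6 within a period gives an SD of the difference of 5.53 to 5.68 in the two-report set, against about 5.44 in completers. The ratio runs from (5.53/5.44) × √(47.8/87.5) = 0.75 to (5.68/5.44) × 0.739 = 0.77, a reduction of 23-25%. The reduction is 12-13% at 95%, about 5% at 98%, and 10% at 90% with ICC 0.3. These ratios do not depend on the assumed SD, and they allow for the noisier means of infants with fewer weeks.

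**5. Power, which is conditional.** At SD 5 and ρ = 0.4:

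- *No dropout, 90% response:* about 48 completers, 70%; about 87 in the two-report set, 90-91%.
- *20% permanent dropout, 95% response:* 55.8 completers, 76.5%; 80.5 in the two-report set, 89.7%.
- *The 35% covers lost families only:* completers = 65 × p^6, because the first online survey is already done. p = 0.99 gives 61 (80%), 0.98 gives 58 (78%), 0.95 gives 48 (70%).
- *The 35% covers any missed survey:* 65 completers remain and power is about 80%. This needs average response of 0.65^(1/7) = 94% per online survey.

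The completer shortfall is sensitive to inputs. With 48 completers, power is 79% at SD 4.5, 87% at SD 4, and 63% to 86% for ρ from 0.3 to 0.6 at SD 5. At 90% response, ICC 0.1 leaves 57 completers (77%) and ICC 0.3 leaves 69 (85%).

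**The case against.** The 1a endpoint is a four-week total, and days in an unreported week are as unknown as product use in that week. The reason given for 2a could therefore be said to carry over. The completer rule is prespecified and clear, the SAP already names the two-report analysis and GEE, and changing *may* to *will* would repair most of the problem without touching the primary analysis. The 65 in section 9.2 may already mean 65 completers, since section 9.3 uses time-points for the two summed periods. Response may also be high: there are reminders, rising payments, and "survey non-respondents who will be contacted by phone twice that day by study staff".

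Part of this stands. For a family with one miss, one of the two totals is incomplete, so using it requires missed weeks to be ignorable within a period. No power deficit and no direction of bias is shown. At 98% response the precision gain is only about 5%. At 90%, 87.5 − 85.3 = 2.2 of the two-report families per 100 were stopped rather than retained.

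It does not rescue the rule. The SAP's own imputation turns a participant's total into four times the mean per reported week, so the SAP already treats that quantity as estimating the total. The completer analysis needs an assumption too: that completers represent everyone else. Even at 98% response, about 11 retained families per 100 are dropped.

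**Conclusion.** The concern holds and should be fixed. The mismatch is plain from sections 4.3, 7.2.1 and 9.3 and does not depend on how the post-intervention condition is read. Its size does depend on response, which the documents do not give. Over 98% to 90% response with independent misses, 11 to 38 retained families per 100 are unused and the standard error could be about 5% to 25% smaller; clustering of misses reduces both. On either reading of the 35%, reports from retained families with a missed survey stay out of the primary comparison. Whether 80% power is at risk turns on that reading, on the SD and correlation, and on clustering, so a shortfall is not claimed. Selection on behaviour after the product starts is built into the rule, but its effect on the estimate cannot be signed.

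**What to change.** 1. In section 9.3, make the primary analysis of 1a **either** the paired comparison of mean rash days per reported week in all participants with at least two reports in each period, **or** the week-level GEE on all reported weeks. Choose one and write that it *will* be done. The precision figures above are for the first.
2. Do the same for average severity in 2b.
3. Keep completers for 2a (any use and number of weeks) and for maximum severity in 2b, because these depend on how many weeks are reported.
4. Keep the completer analysis of 1a as a sensitivity analysis.
5. In section 9.2, state what the 35% covers. Base both that allowance and the trigger for considering 150 participants on the number evaluable for the chosen primary set.

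The cost is SAP wording only: no new data and no method the SAP does not already name. The downsides are slightly noisier means for infants with fewer reported weeks (SD of the difference up from about 5.5 to 5.5-5.7 days at 90% response), a stated assumption that missed weeks are ignorable within a period, and different analysis sets for the two severity measures in 2b. The two-report set reduces selection on behaviour after the product starts but does not remove it.

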1. STUDY OBJECTIVES

1.1 Primary objective: Determine whether parents perceive Theraworx Foam and Spray to be superior to usual care for *prevention* of diaper dermatitis among infants 1-14 months old.

- Hypothesis #1a: Parents will report fewer total days of diaper dermatitis in their infants when the infants are using Theraworx than when they are not.
- Hypothesis #1b: Parents will less likely to report any diaper dermatitis in their infants when the infants are using Theraworx than when they are not.

1.2 Secondary objectives:

Objective #2: Determine whether Theraworx Foam is superior to usual care for reduction of severity of diaper dermatitis among infants 1-14 months old.

- Hypothesis #2a: Parents will report less use of adjuvant topical treatments (antifungals, antibacterials, steroids) for their infant's diaper dermatitis when they are using Theraworx than when they are not.
- Hypothesis #2b: Parents will report less severe diaper dermatitis based on visual assessment when their infants are using Theraworx than when they are not.

Objective #3: Determine parents' satisfaction with Theraworx Foam

- Hypothesis #3a: Parents will find Theraworx easy to apply and remove
- Hypothesis #3b: Parents will find Theraworx pleasant to use (smell, feel, appearance)

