Theraworx Spray Foam by Avadim Health, Inc. is an FDA-registered OTC drug (NDC 61594-000). The marketed product is labelled as a skin protectant with use "for temporary protection of minor cuts, scrapes, burns and chapped or cracked skin" with the active ingredient being allantoin. Allantoin is listed on the FDA OTC Ingredient List as used for or having reviews pending for use as a wound healing agent, skin protectant and external analgesic. As such, Theraworx Foam used in the diaper area may be beneficial for protecting skin against diaper dermatitis wounds, as well as for assisting with wound healing and reducing any associated pain. The purpose of this study is to determine parents' perceptions of the benefits of using Theraworx Spray Foam on their infant's diaper area as part of their hygienic routine, including whether they feel the product is pleasant and easy to use, and whether they feel it helps prevent and reduce the severity of diaper dermatitis in their infants 1-14 months old. This investigation is not intended to be reported to FDA in support of a new indication for use, to support any other significant change in the labeling or to support a significant change in the advertising.

3. PROTCOL DESIGN AND OVERVIEW:

3.1 Study design: This study will be conducted as an open-label, unblinded, sequential trial in which we will employ a pre- vs. post-intervention design involving a run-in period followed by a trial period for all participants. In this way, infants will serve as their own control limiting variability between comparator groups in terms of

diaper hygiene practices including frequency of diaper changes and type of diapers, wipes, and other products used.

3.3 Study Timeline:

	Study month											
Activity	1	2	3	4	5	6	7	8	თ	10	11	12
Recruit and enrollment	Х	х	Х	Х	Х	Х	Х	Х	Х			
Participant run-in period	Х	х	Х	Х	Х	Х	Х	Х	Х			
Participant experimental period		х	Х	Х	Х	Х	Х	Х	Х	х		
Data analysis											х	х

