9. STATISTICAL ANALYSIS PLAN

9.1 Outcome assessment: Outcome of interest will be diaper dermatitis as assessed by parental visual assessment using a modified Diaper Dermatitis Scale Score (see Appendix C).

9.2 Sample size and power calculation: PASS 15 was used to estimate sample size needed to detect a difference of two days of perceived diaper rash between pre- and post-test scenarios using paired t-tests with non-parametric adjustment. Allowing for a large standard deviation of up to 5 days and a moderate degree of correlation between measures, a sample size of 65 with measures at both time-points would allow for detection of statistical difference at 80% power with a two-tailed p-value of 0.05. Assuming a 35% loss to follow up over the 7 weeks participation duration, we plan to recruit 100 participants. If recruitment loss exceeds 35% at the interim, we will consider raising this number to 150 participants.

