Hypothesis 2b: Parents will report less severe diaper dermatitis based on visual assessment when their infants are using Theraworx than when they are not. Dermatitis severity will be considered in two ways: 1) average severity during each study period and 2) maximum severity during each study period. Both average and maximum severity based on the total score from the visual assessment scale will be compared pre- and post-intervention using Wilcoxon signed rank test. As in 1a, for the primary analysis, only participants who completed all 8 weekly surveys will be included. Secondary analyses may consider participants with at least two reports in each of the study periods to allow for severity averages during each study period to be calculated.

Hypothesis 3a: Parents will find Theraworx easy to apply and remove

Hypothesis 3b: Parents will find Theraworx pleasant to use (smell, feel, appearance) Descriptive statistics (median Likert scale scores and proportions) based on parent report will be used to summarize participant satisfaction with Theraworx Spray Foam.

For all analyses, a two-tailed p-value of < 0.05 will be considered significant. Sensitivity analyses based on reported Theraworx Spray Foam use, infant age, and infant sex will be considered. Difference in number of reported diaper rash days between usual care and Theraworx will be compared between high and low Theraworx use groups using Wilcoxon-Mann-Whitney test to assess whether high Theraworx usage improves number of diaper rash days better than low usage More complex longitudinal models considering weekly outcomes during usual care versus Theraworx Spray Foam using Generalized Estimating Equations may also be considered.

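### Two hypotheses sit under the primary objective, each tested at two-sided 0.05, with no order, adjustment or success rule; only the first was sized

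*Combined protocol and SAP*

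**What the plan says.** Section 1.1 states one primary objective, "Determine whether parents perceive Theraworx Foam and Spray to be superior to usual care" for prevention of diaper dermatitis. Two directional hypotheses stand under it without rank: H1a, fewer total days of rash, and H1b, a lower chance of any rash.

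Section 9.3 gives each its own analysis. H1a is compared between periods "using either paired t-test or Wilcoxon signed rank test, as appropriate". H1b goes to McNemar's test (exact or asymptotic is not specified), and there the verb is explore. The section closes with one threshold: "For all analyses, a two-tailed p-value of < 0.05 will be considered significant".

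Section 9.2 sizes the study on "a difference of two days of perceived diaper rash between pre- and post-test scenarios using paired t-tests with non-parametric adjustment" and concludes that "a sample size of 65 with measures at both time-points would allow for detection of statistical difference at 80% power". It gives no power for H1b. Neither section says which hypothesis comes first, whether alpha is shared, or whether the primary objective is met by one significant result or needs two.

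**The concern.** The objective is a superiority claim, so the error that matters is declaring Theraworx better when it is not. One test at two-sided 0.05 carries a 2.5% chance of that. Two tests, either of which may support the claim, carry more.

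If instead both must succeed, that error is not inflated, but the 80% in Section 9.2 is no longer the power for the primary objective. The chance that both succeed cannot exceed the chance that H1a does, and the plan gives no figure for it.

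Because the rule is not written down, it could be settled after the results are known. A report that claimed the primary objective on H1b alone, with H1a not significant, would not contradict the plan as it stands.

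**Working it through.** **1. The plan's own figure.** Section 9.2 gives a difference of 2 days, an SD of up to 5, two-sided 0.05, 80% power, 65 pairs and 35% loss. It calls the correlation moderate and gives no number, so I assume one.

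- SD of the paired difference = 5 × √(2(1 − ρ)).
- ρ = 0.40: SD = 5.48. The paired t-test needs 61 pairs. With the Wilcoxon relative efficiency of 3/π, 61 × π/3 = 63.9, so 64. At 65 pairs the power is 80.8%.
- ρ = 0.45: SD = 5.24. The t-test needs 56 pairs. With the minimum efficiency of 0.864, 56/0.864 = 64.8, so 65.
- Recruitment: 65/(1 − 0.35) = 100.

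The sizing therefore reproduces, and it concerns rash days (H1a) only.

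**2. Either result counts: limits.** Each test has a 0.025 chance of a false result in favour of Theraworx.

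- Independent tests: 1 − (1 − 0.025)² = 0.0494.
- Correlated tests (bivariate normal, r = correlation of the two test statistics): 4.5% at r = 0.5, 4.2% at 0.7, 3.9% at 0.8, 3.5% at 0.9, 3.2% at 0.95.

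**3. Either result counts: simulation.** 65 infants, 4 weeks against 4 weeks as Section 9.3 states, no product effect, no period effect, 8,000 runs per setting. Each infant has its own weekly rash probability, and rash days within a week are drawn from a geometric distribution capped at 7. The rash rates are assumptions. H1a is tested here by paired t; Wilcoxon gives similar results. Entries are the percentage of runs with a significant result in favour of Theraworx.

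| Any rash per period | H1a alone | Either, asymptotic McNemar | Either, exact McNemar |
|---|---|---|---|
| 44% | 2.60 | 4.50 | 3.60 |
| 61% | 2.32 | 4.30 | 3.45 |
| 63% | 2.62 | 4.56 | 3.75 |
| 78% | 2.42 | 4.40 | 3.55 |
| 91% | 2.32 | 4.31 | 3.30 |

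Monte Carlo standard error at 4.5%: √(0.045 × 0.955/8000) = 0.23 points.

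A second model (daily rash onset and duration, 12 settings of 20,000 trials, any rash in 21-84% per period) gives 3.1-3.8% with exact and 3.9-4.8% with asymptotic McNemar. Counting significance in either direction, it gives 6.2-7.7% and 7.8-9.5% against 5%. A wider set of daily-model settings reached 6.0% with asymptotic McNemar, so 3-5% is approximate.

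**4. What the no-period-effect assumption does.** Section 4.2 requires at least one rash in the preceding 2 months, and Section 4.3 excludes infants with a rash on the recruitment day. Both select on a time point next to the usual-care period. When these criteria are added to the daily model, still with no product effect, one set of runs gives about 0.5-1.2% for H1a alone and 1.1-2.3% for either. A wider set of 18 settings gives 0.0-2.7% for H1a alone, and 0.7-4.9% (exact) or 1.3-6.8% (asymptotic) for either. Those runs fill the four usual-care weeks by adding the 7-day recall at baseline (Section 5.3.1) to the 3 run-in weeks, which is itself an assumption.

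**5. What does not depend on the model.** P(H1a or H1b significant) = P(H1a significant) + P(H1b significant and H1a not). The last term is above zero whenever H1b can succeed without H1a.

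**The case against.** The strongest reply is that H1a is the primary hypothesis in all but name. It is listed first, it is the only one sized, Section 9.3 gives it a primary analysis set, and H1b is only to be explored and has no analysis set of its own. The sentence on the threshold says what counts as significant; it does not say that a single significant result establishes the objective. This stands as evidence of intent. It is not a rule: Section 1.1 still files H1b under the primary objective, and the threshold covers every analysis.

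A second reply is that the setting makes the point small. Section 3.1 describes an "open-label, unblinded, sequential trial in which we will employ a pre- vs. post-intervention design", and Section 2 says "This investigation is not intended to be reported to FDA in support of a new indication for use". Lack of blinding and of a concurrent control threaten validity more than this does. That is right and sets the weight, though those limits belong to the design, whereas this one closes with wording.

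A third reply concerns the numbers. A reader might infer that this trial's false-claim rate is 3-5%, or that it necessarily exceeds 2.5%. The documents support neither. They do not say that either result suffices, and the figures need exchangeable periods. With the entry criteria modelled, the either-counts rate can fall below 2.5%. Ageing is a further period effect: Section 2 puts peak incidence at 9-12 months and Section 4.2 enrols at 1-12 months. This objection stands against the absolute rates but leaves the comparison with H1a alone intact.

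**Conclusion.** The gap is real and its weight is minor. Two hypotheses share the primary objective, each at two-sided 0.05, with no order, adjustment or success rule, although the text leans towards H1a. If either may carry the claim, a false claim of benefit is more likely than with H1a alone. At 65 pairs it is about 3-5% against 2.5%, conditional on no product effect, exchangeable periods and assumed rash rates. The relative increase is robust; the absolute rates are not.

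A reader might also look for a power figure under a rule that both must succeed. The documents give no rash rates and do not say whether the effect is on onset or duration, and the answer varies too widely with those assumptions to be useful.

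Section 5.2 has a 3-week run-in, whereas Section 9.3 sums over 4 weeks in each period. That needs reconciling separately; the missing rule is the same under either length.

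**What to change.** Add one or two sentences to Section 9.3, before any outcome data are examined: H1a is the single primary hypothesis; H1b is tested at two-sided 0.05 only if H1a is significant; otherwise H1b is reported as an estimate with a 95% confidence interval and no claim. With no true effect on either outcome, a false claim then requires H1a to be falsely significant, so the error is that of H1a alone.

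H1a's power, the 65 evaluable and the 100 recruited are unchanged. The downside is that H1b cannot support a stand-alone primary claim if H1a fails.

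H1a is proposed because it was sized. Since the objective is prevention and H1b measures occurrence directly, the order remains the sponsor's choice. Declaring H1b supportive would also remove the ambiguity. Requiring both would do so too, but needs a new power statement. Splitting alpha at 0.025 each costs more: H1a's power falls from 80% to about 71% at 65 pairs, and restoring it takes 79 pairs, or 79/0.65 = 121.5, so 122 recruited.
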